Name:	[REDACTED]
Address:	UCB Biosciences Inc. [name], [REDACTED] Morrisville, NC 27560 USA
Phone:	[REDACTED]
Email:	[REDACTED]

Clinical Project Manager

Name:	[REDACTED]
Address:	UCB Biosciences Inc. [name], [REDACTED] Morrisville, NC 27560 USA
Phone:	[REDACTED]
Email:	[REDACTED]

Clinical Trial Biostatistician

Name:	[REDACTED]
Address:	UCB Biosciences Inc. [name], [REDACTED] Morrisville, NC 27560 USA
Phone:	[REDACTED]
Email:	[REDACTED]

Change #2

Section 4, Study variables

Baseline values from SP1006 will serve as Baseline in RL0007.

Has been changed to:

Baseline values from SP1006 will serve as Baseline in RL0007. Baseline values for the other safety variables were collected at Visit 1 of SP1006.

Change #3

Section 4.1.2, Other safety variables

- Changes from Baseline in 12-lead ECGs
- Changes from Baseline in vital signs (including assessment of orthostasis)
- Changes from Baseline in hormone status
- Changes from Baseline in laboratory data (hematology, clinical chemistry, and urinalysis)
- Changes from Baseline in menstrual function for all female subjects
- Changes in mMIDI
- Changes from Screening in body weight, height, and BMI

Has been changed to:

- Changes from Baseline (Visit 1, SP1006) in 12-lead ECGs
- Changes from Baseline (Visit 1, SP1006) in vital signs (including assessment of orthostasis)
- Changes from Baseline (Visit 1, SP1006) in hormone status
- Changes from Baseline (Visit 1, SP1006) in laboratory data (hematology, clinical chemistry, and urinalysis)
- Changes from Baseline in menstrual function for all female subjects
- Changes in mMIDI
- Changes from Baseline (Visit 1, SP1006) in body weight, height, and BMI

Change #4

Section 7.5, Handling and storage requirements

First and fourth paragraphs

Rotigotine transdermal patches should be stored in the original pouch. Rotigotine should be stored according to the labeling on the clinical trial supply packaging. The investigator (or designee) is responsible for the safe and proper storage of rotigotine at the site. Rotigotine stored by the investigator is to be kept in a secured area with limited access according to the storage conditions mentioned on the label.

As part of the remote study model, the study site will provide study medication and all required supplies via direct-to-subject shipments. Once eligibility is confirmed, the study site will contact the interactive response technology (IRT), and shipments will be prepared and sent out for delivery to the subject's/legal representative's home/preferred address. Shipments will be confirmed as delivered by the study staff, with appropriate documentation in the subject's study records. The study medication will be confirmed as received in good condition and within the acceptable temperature range (ie, fit for use). A telemedicine call will be completed to instruct the subject/legal representative on the correct storage and administration of the study medication, which will also be documented as part of subject's study record.

Has been changed to:

Rotigotine transdermal patches should be stored in the original pouch. Rotigotine should be stored according to the labeling on the clinical trial supply packaging. The investigator (or designee) is responsible for the safe and proper storage of rotigotine at the site. Rotigotine stored by the investigator (or designee) is to be kept in a secured area with limited access according to the storage conditions mentioned on the label.

As part of the remote study model, the study site's depot/pharmacy will provide study medication and all required supplies via direct-to-subject shipments. Once eligibility is confirmed, the study site will contact the interactive response technology (IRT), and shipments will be prepared and sent out for delivery to the subject's/legal representative's home/preferred address. Shipments will be confirmed as delivered by the study staff, with appropriate documentation in the subject's study records. The study medication will be confirmed as received in good condition and within the acceptable temperature range (ie, fit for use). A telemedicine call will be completed to instruct the subject/legal representative on the correct storage and administration of the study medication, which will also be documented as part of subject's study record.

Change #5

Section 7.6, Drug accountability

First and third paragraphs

At the designated timepoints during the study, subjects/legal representatives will return to the study site the unused study medication patches remaining as part of the medication kits, along with the kit itself, via the return shipment materials provided. A Drug Accountability form will be used to record IMP dispensing and return information on a by subject basis and will serve as source documentation during the course of the study. Details of any IMP lost, damaged (due to breakage or wastage), not used, disposed of at the study site, or returned to the Sponsor or designee must also be recorded on the appropriate forms. All supplies and drug accountability documentation must be made available throughout the study for UCB (or designee) to review.

The investigator may assign some of the investigator's duties for drug accountability at the study site to an appropriate designee.

Has been changed to:

At the designated timepoints during the study, subjects/legal representatives will return to the study site's depot/pharmacy the unused study medication patches remaining as part of the medication kits, along with the kit itself, via the return shipment materials provided. A Drug Accountability form will be used to record IMP dispensing and return information on a by subject basis and will serve as source documentation during the course of the study. Details of any IMP lost, damaged (due to breakage or wastage), not used, disposed of at the study site's depot/pharmacy, or returned to the Sponsor or designee must also be recorded on the appropriate forms. All supplies and drug accountability documentation must be made available throughout the study for UCB (or designee) to review.

The investigator may assign some of the investigator's duties for drug accountability at the study site's depot/pharmacy to an appropriate designee.

Change #6

Section 7.7, Procedures for monitoring subject compliance

First paragraph

At the designated visits (see [Table 5-1](#)), subjects/legal representatives will return all unused IMP and empty IMP containers, using the return shipment supplies provided to them by the study staff. Upon receipt of the returned medication at the study site, the designated study staff will review drug accountability with the subject/legal representative via a telephone or a telemedicine call in order to obtain explanations regarding any discrepancies in compliance with the dosing regimen.

Has been changed to:

At the designated visits (see [Table 5-1](#)), subjects/legal representatives will return all unused IMP and empty IMP containers, using the return shipment supplies provided to them by the study staff. Upon receipt of the returned medication at the study site's depot/pharmacy, the designated study staff will review drug accountability with the subject/legal representative via a telephone or a telemedicine call in order to obtain explanations regarding any discrepancies in compliance with the dosing regimen.

10.3.1	Elevated liver function tests.....	19
10.4	Vital signs, physical findings, and other observations related to safety	19
10.4.1	Vital signs	19
10.4.2	Electrocardiograms	20
10.4.3	Modified Minnesota Impulsive Disorders Interview.....	20
10.4.4	Physical and neurological examinations.....	20
10.4.5	Suicide ideation and behavior.....	20
11	OTHER ANALYSES	20
11.1	Subject Quality of Life Questionnaire.....	20
12	REFERENCES	22
13	APPENDICES.....	23
13.1	Amendment 1	23
	STATISTICAL ANALYSIS PLAN SIGNATURE PAGE.....	24

LIST OF ABBREVIATIONS

AE	adverse event
ARDL	actual Rotigotine dose level
BMI	body mass index
C-SSRS	Columbia Suicide Severity Rating Scale
CGI	Clinical Global Impressions
eCRF	electronic Case Report form
ECG	12-lead electrocardiograms
EoM	end of the Maintenance Period
FDA	Food and Drug Administration
FSH	follicle-stimulating hormone
HLT	High Level Term
ICH	International Council for Harmonization
IGF-1	insulin-like growth factor 1
IRLS	International Restless Legs Syndrome Study Group Rating Scale
LH	luteinizing hormone
MedDRA	Medical Dictionary for Regulatory Activities
mMIDI	Modified Minnesota Impulsive Disorder Interview
PD	pharmacodynamic
PDILI	potential drug induced liver injury
PK	pharmacokinetic
PKS	Pharmacokinetic Set
PRD	planned Rotigotine dose
PRDL	planned Rotigotine dose level
PT	preferred term
RLS	Restless Legs Syndrome
RLS-6	Restless Legs Syndrome - 6 Rating Scales
RLS-QoL	restless legs syndrome quality of life
SAP	Statistical Analysis Plan
SD	standard deviation
SOC	System Organ Class
SoM	Start of Maintenance Period
SS	Safety Set

T3	triiodothyronine
T4	thyroxine
TEAE	treatment-emergent adverse event
TSH	thyroid-stimulating hormone
WHO-DD	World Health Organization Drug Dictionary

This document cannot be used to support any marketing authorization application and any extensions or variations thereof.
PUBLIC COPY

1 INTRODUCTION

This document contains details for the statistical analyses of study RL0007 supporting the clinical study report which has been written in consideration of the International Council for Harmonization (ICH)/Food and Drug Administration (FDA) E9 Guidance documents (Phillips et al, 2003). The reader is referred to the study protocol and the electronic Case Report form (eCRF) for details of study conduct and data collection.

The SAP describes the statistical principles that are applied for the analyses as well as tables and listings that are foreseen for this study. Changes in the statistical methodology result in a SAP amendment. Amendments to this document will be finalized prior to database lock.

This study was terminated early, and therefore the analysis described in this analysis plan is much more limited than that described in the protocol.

2 PROTOCOL SUMMARY

2.1 Study objectives

The primary objective of this study is to assess the long-term safety and tolerability of rotigotine treatment in adolescents with idiopathic Restless Legs Syndrome (RLS).

The secondary objective of this study is to assess the long-term efficacy of rotigotine treatment in adolescents with idiopathic RLS.

2.1.1 Efficacy variables

2.1.1.1 Secondary efficacy variables

The key efficacy variables are change from Baseline at Visit 9 in International Restless Legs Rating Scale (IRLS) sum score, Clinical Global Impressions (CGI) Item 1 and Restless Legs-6 Rating Scales (RLS-6):

- Changes from Baseline in IRLS sum score at Visit 9
- Changes from Baseline in CGI Item 1 at Visit 9
- Changes from Baseline in RLS-6 at Visit 9

2.1.1.2 Other efficacy variables

Other efficacy variables are:

- Changes from Baseline in IRLS sum score at all visits except Visit 9
- Changes from Baseline in CGI Item 1 at all visits except Visit 9
- Changes from Baseline in RLS-6 at all visits except Visit 9

2.1.2 Safety variables

2.1.2.1 Primary safety variables

The primary safety variables are:

- Occurrence of treatment-emergent adverse events (TEAEs)
- TEAEs leading to permanent withdrawal of study medication

2.1.2.2 Other safety variables

Other safety variables are:

- Changes from Baseline in 12-lead electrocardiograms (ECGs)
- Changes from Baseline in vital signs (including orthostatic assessment)
- Changes from Baseline in hormone status
- Changes from Baseline in laboratory data (hematology, blood chemistry, and urinalysis)
- Changes in menstrual function for all female subjects
- Changes from Baseline in Modified Minnesota Impulsive Disorder Interview (mMIDI)
- Changes from Baseline in body weight, height, and calculated body mass index (BMI)

2.1.3 Other variables

Other variables are:

- Plasma concentrations of unconjugated rotigotine
- Subject Quality of Life Questionnaire

2.2 Study design and conduct

This is a Phase 3, remote, open-label, LTFU study of monotherapy administration of the rotigotine transdermal system. Subjects entering this study from the previous rotigotine study in adolescents (SP1006) must have tolerated the first dose level of rotigotine in that study without meeting the withdrawal criteria.

The study will be conducted using the remote study model, which uses telemedicine technology (i.e., Science 37 PLATFORM) for interactions between the investigator/study staff and study subjects/legal representatives.

The study will begin with a Titration Period of up to 3 weeks (at maximum) with the aim of achieving the individually optimized dosage. During the Titration Period, investigators should determine at each visit whether the subject has reached his or her optimal dose prior to completing the scheduled assessments. Once subjects have reached their optimal dose, they should proceed to Maintenance Period (Visit 5) and complete those assessments.

Titration will be followed by a Maintenance Period of up to 1 year. Dose adjustment of rotigotine is allowed at any time during the Maintenance Period, based on clinical judgment up to a maximum dose of 3mg/24h. At the End of Maintenance (EoM), subjects will enter a 4-day Taper Period followed by a 30-day Safety Follow-Up.

Visits will be scheduled every week during the Titration Period, every 3 months for the Maintenance Period, and at the end of the Safety Follow-Up.

2.3 Determination of sample size

No statistical sample size calculation was performed for this study. Initially, a maximum of 138 subjects from a prior study (SP1006) are expected to participate in the current study, based on the assumption that all planned subjects from SP1006 will roll-over into the present study.

3 DATA ANALYSIS CONSIDERATIONS

3.1 General presentation of summaries and analyses

Statistical analysis and generation of tables, figures, subject data listings, and statistical output will be performed using SAS Version 9.3 or higher. All tables and listings will use Courier New font size 9.

A complete set of raw data listings containing both all documented data and all calculated data (eg, changes from Baseline) will be generated.

Unless otherwise noted, all summaries will be displayed by the final dose group (rotigotine 1mg/24h, rotigotine 2mg/24h and rotigotine 3mg/24h). The ‘final dose’ is the final titrated or back-titrated dose level administered at the start of the Maintenance Period. The ‘final dose’ for subjects who withdrew before the Maintenance Period is defined as the last dose taken. A summary with all dose groups combined (i.e., total column) will be presented for the demographic and Baseline characteristics, and for the prior and concomitant medications.

In general, summary statistics for quantitative variables will include n (number of available measurements), arithmetic mean, SD, median, minimum, and maximum. For categorical parameters, descriptive statistics will consist of the number and percentage of subjects in each category. Unless otherwise specified the denominator for calculating percentages will be the number of subjects in the respective population.

Unless otherwise noted, all percentages with the exception of 0 and 100 will be expressed to 1 decimal place. 100% will be presented as integer. If a category has the frequency 0 the percentage value will be omitted. Mean and median changes from baseline lower than the minimal displayable change will be displayed without sign (e.g., -0.00 will be displayed as 0.00).

For descriptive statistics, the following rules regarding decimal places will apply:

- n will be an integer.
- Mean, SD, and median will use 1 additional decimal place compared to the original data.
- Minimum and maximum will have the same number of decimal places as the original value.

Unless otherwise noted, listings will be sorted by optimal dose, site-subject number, parameter (if applicable) and time point (if applicable). All listings will include assessments on scheduled and unscheduled visits; data from unscheduled visits will appear in chronological order together with the scheduled time points – a repeated measurement will appear directly after the time point for which the repeat measurement was performed.

In individual subject data listings, values are presented as documented in eCRF using the same number of digits. Derived data are presented with 1 digit more than the original data used in the derivation. Dates are presented as documented without imputing incomplete dates.

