3.5.2 Safety Set

The Safety Set (SS) will consist of all subjects who have at least one patch (rotigotine) applied. This analysis set will be used for all analyses except for the pharmacokinetic data.

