10 SAFETY ANALYSES

All safety analyses will be conducted for the SS and results will be presented by final dose group and for all subjects combined.

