10.3 Clinical laboratory evaluations

The following laboratory parameters are measured within the study:

- Hematology parameters: Hematocrit (HCT), Hemoglobin (HGB), Platelets (PLAT), Red Blood Cells (RBC), White Blood Cells (WBC), and differential count and percentile (Lymphocytes, Basophils, Eosinophils, Monocytes, Neutrophils)
- Liver Function Tests and other Chemistry parameters: Alanine Aminotransferase (ALT), Aspartate Transaminase (AST), Albumin, Alkaline Phosphatase (ALP), Bicarbonate (Total CO₂), Blood Urea Nitrogen (BUN), Calcium, Chloride (CL) Creatinine, Ferritin, Gamma-glutamyl transferase (GGT), Glucose, Iron Binding Capacity Total (IBCT), Iron Binding Capacity Unsaturated (IBCU), Lactate Dehydrogenase (LDH), Potassium, Phosphorus, Serum Iron, Sodium, Total cholesterol, Total bilirubin, Total protein, Transferrin, Uric acid
- Endocrine parameters: Estradiol (females only), Follicle-stimulating Hormone (FSH), Insulin-like Growth Factor 1 (IGF-1), Luteinizing Hormone (LH), Progesterone (females)

only), Prolactin, Testosterone (males only), Thyroxine Free (T4FR), Triiodothyronine (T3), Thyroid Stimulating Hormone (TSH)

- Endocrine normal ranges are provided by the central lab and included in the dataset specifications.
- Urinalysis: Color, Appearance, Glucose, Protein, Blood, Ketones, Urine Pregnancy Test

Summary statistics of the observed values and their change from Baseline and the frequency of abnormal values based on normal ranges will be presented by visit for laboratory parameters of hematology, chemistry and endocrinology.

Laboratory data outside the reference range will be highlighted with “L” for low and “H” for high in all laboratory subject data listings where applicable.

Individual subject data listings will be presented for laboratory parameters of hematology, chemistry and endocrinology. Urinalysis and pregnancy test results will only be listed.

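### By-visit laboratory abnormality percentages are understated, because the default denominator is the whole Safety Set, including subjects without a result and subjects of the other sex

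*SAP*

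**What the plan says.** - **Form of categorical summaries (SAP 3.1).** "For categorical parameters, descriptive statistics will consist of the number and percentage of subjects in each category".
- **Default denominator (SAP 3.1).** "Unless otherwise specified the denominator for calculating percentages will be the number of subjects in the respective population".
- **Population for safety tables (SAP 10).** "All safety analyses will be conducted for the SS and results will be presented by final dose group and for all subjects combined". The Safety Set "will consist of all subjects who have at least one patch (rotigotine) applied" (SAP 3.5.2). Membership does not depend on having a laboratory result, or on sex.
- **The table in question (SAP 10.3).** Besides summary statistics, "the frequency of abnormal values based on normal ranges will be presented by visit for laboratory parameters of hematology, chemistry and endocrinology". No denominator is given. The same section limits estradiol and progesterone to females and testosterone to males.
- **Timing (Protocol Table 5-1).** Safety laboratory tests are scheduled at Visits 5, 7 and 9, and hormone status at Visits 5 and 9.
- **Early stop (SAP 1).** "This study was terminated early, and therefore the analysis described in this analysis plan is much more limited" than the protocol's.

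Nothing elsewhere overrides the default for this table. Protocol 13.2 mentions frequency tables for qualitative data but sets no denominator.

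**The concern.** A by-visit abnormality rate is normally read as the proportion abnormal among those tested at that visit. Under the SAP's default, a subject with no result stays in the denominator and is in effect counted as not abnormal. This has two separate consequences.

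1. **Loss over time.** As fewer subjects have a result, the printed percentage shrinks even if the rate among those tested is constant. The study's primary objective is long-term safety, so the late visits are the informative ones. After an early stop they may also be the sparsest.
2. **Sex-specific hormones.** Dividing a female-only or male-only count by both sexes lowers the percentage at every visit, including Visit 5 with nobody lost.

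The final-dose columns can be affected too. SAP 3.1 assigns a subject who withdrew before Maintenance to the last dose taken. That subject remains in the column's denominator at Visits 7 and 9, so columns can differ through retention alone. The study has one arm and is descriptive, so no comparator or model would correct the percentage.

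**Working it through.** The plan states no rate or power figure to reproduce. Its 138 is a roll-over ceiling, not a calculated sample size. The check is direct arithmetic.

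**Inputs**
- From the documents: the denominator is the Safety Set or final-dose group, N; the table is by visit; three hormones are sex-specific.
- Assumed, because the documents give no values: p, the abnormality rate among assessed subjects; r, the share of eligible subjects with a result at the visit; f, the share of the group of the applicable sex (f = 1 for parameters measured in everyone).

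**Formula**
- Assessed subjects = N × f × r. Abnormal subjects = p × N × f × r.
- Printed percentage = (p × N × f × r) / N = p × r × f.
- Percentage among assessed = p.
- N cancels, so the understatement factor r × f does not depend on the size of the Safety Set.

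**Loss only (p = 20%, f = 1)**
- r = 0.6: 20% × 0.6 = 12%
- r = 0.4: 20% × 0.4 = 8%
- r = 0.3: 20% × 0.3 = 6%

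**Sex only (p = 20%, r = 1)**
- f = 0.4: 20% × 0.4 = 8%
- f = 0.5: 20% × 0.5 = 10%
- f = 0.6: 20% × 0.6 = 12%

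**Both:** with f = 0.5 and r = 0.3, 20% × 0.5 × 0.3 = 3%.

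**Trend.** The printed rate falls from visit a to visit b whenever p_b / p_a is smaller than r_a / r_b. For illustration, take N = 138 and assume 130, 70 and 30 subjects assessed.

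| Visit | Assessed | Abnormal | Rate among assessed | Printed (abnormal / 138) |
|---|---|---|---|---|
| 5 | 130 | 13 | 10.0% | 9.4% |
| 7 | 70 | 10 | 14.3% | 7.2% |
| 9 | 30 | 9 | 30.0% | 6.5% |

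A rate that triples among those tested is printed as falling. With the same numbers assessed and a constant 20% (26, 14 and 6 abnormal), the printed values are 18.8%, 10.1% and 4.3%. The sex factor f is roughly constant over visits, so it lowers the level but does not by itself create a trend.

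**The case against.** **The text may not mean Safety Set percentages.** SAP 10.3 promises a frequency, and SAP 3.1 itself uses that word for a count when it says how to print empty categories. Population is not a defined term, since SAP 3.5 defines sets. The sex labels could be read as naming the population for those hormones. This leaves some room. But SAP 3.1 attaches a percentage to every categorical summary, SAP 10 names the Safety Set for all safety analyses, and SAP 10.3 states no exception. Safety Set percentages remain the plain reading, and under any other reading the denominator is unspecified and needs the same sentence.

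**The rate can be rebuilt.** This stands. SAP 3.1 puts counts beside percentages. SAP 10.3 plans quantitative summaries of the same parameters by visit, and these show n of available measurements. Listings flag low and high values for each subject, and SAP 10.3.1 lists elevated liver tests separately. A reader might infer that the rule hides late abnormalities. The documents do not support that: the percentage is too low, but no abnormal value is lost. Still, the SAP does not require n in the abnormality table itself.

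**Leavers can still contribute.** This also stands. A Withdrawal Visit repeats the Visit 9 procedures, including safety laboratory tests and hormones (Protocol 8.3.4 and 8.6), and SAP 4.2 attributes off-schedule discontinuation data to the next scheduled visit. A subject who leaves between Visits 6 and 7 can therefore count at Visit 7. It would be wrong to say that only subjects still in the study enter the later numerators. The rule delays the dilution and does not remove it.

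**The table is secondary.** Laboratory and hormone changes are other safety variables (SAP 2.1.2.2). The primary ones are treatment-emergent adverse events and those leading to permanent withdrawal of study medication, for which the Safety Set is the natural denominator. No test or decision rule uses the laboratory percentages.

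**Conclusion.** The point holds at moderate severity. Following the SAP as written, by-visit percentages of abnormal laboratory values equal the rate among assessed subjects times r, and times r × f for estradiol, progesterone and testosterone. The direction is certain whenever some subjects lack a result or the group contains both sexes. The trend over visits can be distorted, and in some configurations reversed.

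The size in this study is unknown, because the documents do not report how many subjects were treated, how many were assessed at each visit, or the sex split. Every figure above rests on assumed values of p, r and f. A reader might infer that this study's late rates were understated by a known amount, or that the error is serious enough to undermine the primary safety results. The documents support neither. The primary variables are untouched, and the correct rate can be recovered from the count and the n for the same parameter and visit.

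**What to change.** Add one sentence to SAP 10.3, for example: percentages of abnormal values at a visit are based on the subjects in the group, of the applicable sex for sex-specific hormones, who have a non-missing result for that parameter at that visit, including withdrawal data attributed to the visit under SAP 4.2; the table shows the abnormal count over this number (n/Nobs).

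With this denominator the assumed 20% prints as 20% at every visit and for every hormone, and the shown Nobs makes sparse late visits visible.

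The cost is one SAP sentence and a denominator change in one table programme. No new data are needed. SAP 1 allows amendments up to database lock.
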